## **Macrophage Markers in Periodontal and Peri-implant Health and Disease (NCT05242354)**

### **Study protocol**

#### *Background*

CD80, CD163 and CD206 have been used in prior research in specifying macrophage phenotypes in periodontal and peri-implant tissues (1-5). However, there are no previously published studies on total gingival levels of CD163, CD206 and CD80 comparing peri-implantitis, periodontitis, peri-implant health and periodontal health.

#### *Primary objective*

- to reveal the differences in CD163, CD206 and CD80 tissue levels between peri-implantitis, periodontitis, peri-implant health and periodontal health

#### *Subject population (n=36)*

- applied to Biruni University between March-December 2021
- systemic healthy and  $\geq 18$  years-old non-smokers with no regular medicine intake who are willing to participate
- no antibiotics or anti-inflammatories for the last 3 months
- not pregnant, not in lactation
- according to the healthy or diseased groups:
  - diagnosed with peri-implantitis or generalized Stage III periodontitis - at least one BoP+ periodontal/peri-implant pocket with a PPD of 6 – 10 mm
  - periodontally healthy in need of crown lengthening, gingivectomy, tooth extraction or dental implant application (having no pockets with PPD  $\geq 4$  mm and having a full mouth score of BoP < 10%)
  - having a submerged implant, which is partially exposed and has no visible signs of inflammation

### *Clinical data*

Probable pocket depth, indirect clinical attachment loss, and bleeding on probing from six sites of all teeth / implants

### *Tissue samples*

- Periodontitis and peri-implantitis samples – during non-surgical therapy with a single stroke using Gracey curette
- Healthy peri-implant mucosa – during implant exposure surgery with an incisional biopsy
- Healthy gingiva – during the corresponding treatment with a crestal incision reaching the bottom of the crevice.

### *Quantification of CD163, CD206 and CD80*

- grinding of tissues with a high-speed tissue homogenizer
- protein determination with a commercial protein determination kit
- immunoblot analysis of each sample according to their total protein counts
- quantification of the band intensities

### *Statistics*

- Kruskal-Wallis test – to reveal the differences of CD163, CD206 and CD80 levels (arbitrary units) between groups (peri-implantitis, periodontitis, peri-implant health, periodontal health)
- Mann Whitney U test – pairwise comparison of groups showing significant differences according to Kruskal-Wallis test.
- Chi-square – qualitative variables
- $p < 0.05$  – significant

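### If a marker's samples occupy more than one blot, the planned rank tests pool uncalibrated band intensities with nothing to put the blots on one scale

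*Combined protocol and SAP*

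**What the plan says.** The primary objective is "to reveal the differences in CD163, CD206 and CD80 tissue levels" among four groups. The assay section (Quantification of CD163, CD206 and CD80) ends with "immunoblot analysis of each sample according to their total protein counts" and then "quantification of the band intensities". The Statistics section applies a Kruskal-Wallis test "to reveal the differences of CD163, CD206 and CD80 levels (arbitrary units) between groups" and a Mann-Whitney U test for "pairwise comparison of groups showing significant differences according to Kruskal-Wallis test", at a 0.05 threshold. Neither test is stratified.

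The Subject population section gives 36 subjects. It does not give group sizes or samples per subject. No section states the gel format, the number of blots per marker, how groups are placed on blots, or whether a common reference is run on each blot.

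**The concern.** Band intensity in arbitrary units has no external calibration. Standardising by total protein, whether by equal loading or by division, deals with how much material is in each lane. It does not remove differences between blots in transfer, antibody binding or exposure. If a marker's samples occupy several blots, one ranking of all values treats a bright blot as high expression.

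The consequence depends on the layout. Where blots follow groups, fully or in part, blot differences are read as group differences. Where groups are spread over blots, the blot differences act as noise. These tests are the only analysis of the only primary objective, and all three markers are measured this way.

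**Working it through.** The plan states no power, effect size or SD, so there is no figure of its own to reproduce. The check is a simulation of the planned test.

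**From the documents:** 36 subjects, four groups, Kruskal-Wallis test, threshold 0.05.

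**Assumed:**
- one sample per subject and 36/4 = 9 per group;
- three blots of 36/3 = 12 samples;
- normal data with within-blot SD 1 (this includes variation between subjects);
- a random additive shift per blot with SD *r* = 0.25, 0.5 or 1.0;
- for power, a 1.2 SD shift in both disease groups.

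The blot share of total variance is r²/(1 + r²): 0.0625/1.0625 = 6%, 0.25/1.25 = 20% and 1/2 = 50%. The documents give no value for r.

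**Test:** H = 12/(N(N+1)) × Σ(Rₖ²/9) − 3(N+1), where N = 36 and Rₖ is the rank sum of group k, referred to chi-square with 3 df. There were 20,000 runs per cell. A repeat of the main cells with 40,000 runs agreed to within about one percentage point.

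**False-positive rate of the planned Kruskal-Wallis test**

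| Layout | r = 0 | 0.25 | 0.5 | 1.0 |
|---|---|---|---|---|
| One blot per group (extreme) | 4.5% | 14.1% | 42.3% | 81.8% |
| Three blots filled in group order | 4.4% | 9.4% | 25.0% | 58.4% |
| Partly aligned (four blots, 6 of each 9 on one blot) | – | 6.4% | 11.5% | 26.1% |
| Random, three blots, averaged over layouts | 4.4% | 4.3% | 4.4% | 4.4% |
| Balanced, three blots | 4.5% | 4.0% | 2.5% | 1.4% |

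In group order, the Mann-Whitney comparison of the first with the last group, made only after a significant Kruskal-Wallis test, is falsely positive in 4.3%, 15.9% and 42.7% of runs, against 1.6% with no blot effect.

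The random row is an average. Over 150 fixed random layouts (2,000 runs each), the 95th percentile of the error rate was about 9% at r = 1.0 (maximum 16%) and about 6.5% at r = 0.5 (maximum 9%). At r = 0.25 the effect was negligible.

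**Power of the planned Kruskal-Wallis test, three blots**

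| Layout | r = 0 | 0.25 | 0.5 | 1.0 |
|---|---|---|---|---|
| Balanced | 78.9% | 76.3% | 69.8% | 48.9% |
| Random | 78.7% | 77.0% | 71.2% | 57.1% |

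The balanced losses are 78.9 − 76.3 = 2.6, 78.9 − 69.8 = 9.1 (about 8 in repeat runs) and 78.9 − 48.9 = 30.0 points. The random losses are 1.7, 7.5 and 21.6 points.

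**Blot-stratified (van Elteren type) test.** Power on three balanced blots is 75.4-76.0% at every r. It overtakes the planned test at r of about 0.3 (planned 76.0%, stratified 75.7%). On three random blots it is 72.2-72.5%, and the crossing lies between 0.45 (72.6% against 72.1%) and 0.5 (71.3% against 71.9%). On group-order blots it is only 23.0-23.7%, because few groups share a blot.

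**Ratio to a common reference.** With an assumed reference-lane error of 0.1, 0.25 or 0.5 SD, three balanced blots and no blot effect, power is 78.5%, 76.6% and 70.3%. With one blot per group the false-positive rate is 5.8%, 13.6% and 42.4%, because the error of the reference then follows the group. With random allocation it stays at 4.2-4.6%.

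**The case against.** The strongest reply is that nothing here is shown to be wrong. The assay section is a four-line summary, Kruskal-Wallis on arbitrary units is not wrong in itself, and harm needs two facts that the documents do not give: more than one blot per marker and, for bias, blots that track groups. That stands, and the point is conditional on both.

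A reader might infer that the trial's false-positive rate is inflated. The documents do not support that, because no layout is described. A reader might equally infer that power is the only cost whenever groups are not deliberately aligned. That is also too strong: partial alignment biases the test, and random allocation protects only on average.

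Three further objections hold in part. The largest effects sit at r = 1.0, where blots supply half the variance; at 0.25 the cost under balanced or random layouts is about 2-3 points. The assays may already be done, since subjects "applied to Biruni University between March-December 2021", but that dates recruitment and no assay date is given. Diseased tissue comes from one curette pass, so there may be too little protein for a pooled reference or a re-run.

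None of this reduces the point to a request for missing detail. An even loading plan costs almost nothing and closes the route to bias.

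**Conclusion.** The concern holds conditionally. With one sample per subject and more than one blot per marker, the plan ranks intensities across blots without a common scale. Full or partial alignment of blots with groups raises false positives; a balanced layout costs only power. The directions do not depend on the assumed SD ratio. The sizes do, and they also rest on 9 per group, three blots, normal data and, for power, the 1.2 SD shift. The documents neither describe an aligned layout nor exclude one. The change should be made, with medium confidence because the number of blots is unknown.

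**What to change.** **Before blots are run.** For each marker, spread all four groups as evenly as possible over every blot. Then pre-specify one of two analyses before group results are seen:
- Blot-stratified rank tests of van Elteren type. If there is in fact no blot effect, this loses about 2-5 points of Kruskal-Wallis power on two to four balanced blots, and about 5 points (56.1% to 50.9%) for a gated Mann-Whitney comparison of disease with health on three.
- If protein yield allows, the ratio to a common reference sample run on every blot, analysed with the planned tests. This takes one lane per blot plus protein for the reference, and loses about 0-9 points depending on reference error. Groups must not be aligned with blots; an even spread is desirable but not strictly required for validity.

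No extra subjects are needed.

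**If blots are already run.** Report the number of blots per marker, the group layout and any reference. Keep the planned test, and add the blot-stratified test as a sensitivity analysis where groups share blots. On randomly filled blots that test loses about 3, 6 or 10 points for two, three or four blots if there is no blot effect; on three it gains about 15 points at r = 1.0. If blots follow groups, state that blot and group effects cannot be separated.

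If all samples for a marker share one blot, one sentence saying so closes the point.

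### The pairwise Mann-Whitney tests have no multiplicity correction; with four groups the Kruskal-Wallis gate lets the per-marker error reach about 8–12.5% when groups clearly differ but two or three truly equal pairs remain

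*Combined protocol and SAP*

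**What the plan says.** The Primary objective section sets one aim: "to reveal the differences in CD163, CD206 and CD80 tissue levels between peri-implantitis, periodontitis, peri-implant health and periodontal health". The Statistics section is the whole analysis plan. It gives the Kruskal-Wallis test "to reveal the differences of CD163, CD206 and CD80 levels (arbitrary units) between groups", so there is one omnibus test per marker over four groups. The Mann-Whitney U test then serves for "pairwise comparison of groups showing significant differences according to Kruskal-Wallis test". I read this as: for each marker with a significant omnibus result, compare the groups in pairs.

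The only threshold is p < 0.05. No adjustment is named anywhere in the document, and the pairwise results are not labelled exploratory. The Subject population section gives a total of 36 and no group sizes.

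**The concern.** Kruskal-Wallis can say that the four groups are not all alike, but not which ones differ. Every statement about a particular pair therefore rests on an unadjusted Mann-Whitney test. Testing pairs only after a significant omnibus test controls the error for all pairs when there are three groups, but not when there are four.

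The exposed situation is a natural one here, because the design has two diseased and two healthy groups. If disease shifts a marker, the gate opens almost automatically. Peri-implantitis against periodontitis, and healthy peri-implant against healthy gingival tissue, are then each tested at 0.05 with nothing further to protect them. The Background section presents the four-way comparison as the gap to be filled, so a false difference between the two diseases would be read as a main finding.

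**Working it through.** **Inputs from the document.** Threshold 0.05, three markers, four groups, Kruskal-Wallis then Mann-Whitney, no correction (Statistics); 36 participants (Subject population).

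**Assumptions.** 36/4 = 9 per group; two-sided tests; normal data with equal SD and a shift between groups. Log-normal intensities shifted on the log scale give the same result, because only ranks are used. The plan does not say whether Mann-Whitney p-values are exact or approximate, so both were run (the approximation without continuity correction).

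**1. Number of tests.** 4 × 3 / 2 = 6 pairs per marker; 6 × 3 = 18 in all.

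**2. The plan's own figure.** The only error figure is 0.05. No power, effect size or SD accompanies the 36, so there is no sample-size calculation to reproduce. If no groups differ, a false pairwise claim needs the gate to open, and the simulated error is about 4.5%. In that case 0.05 is respected.

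**3. Why four groups are different.** With three groups, either all are equal (the gate protects) or at most one equal pair exists (a single test at 0.05). Four groups add two patterns: two equal pairs that differ from each other, and three equal groups with one apart.

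**4. Analytic size once the gate is open.**
- Two equal pairs share no group, so their tests are independent and the error is 1 − (1 − a)². At a = 0.05 this is 1 − 0.95² = 9.75%.
- With 9 per group the exact test rejects at U ≤ 17, true size 0.0400: 1 − 0.96² = 7.8%. The approximation rejects at U ≤ 18 (p = 0.0469), true size 0.0503: 1 − 0.9497² = 9.8%.
- Three equal groups: the probability that the studentized range of three means exceeds 1.96 × √2 is 12.2%.

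**5. Simulation of the plan as written** (40,000 to 60,000 studies per setting; chance of at least one false pairwise difference within a marker):

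| True pattern | Gate opens | Exact | Approximate |
|---|---|---|---|
| No differences | 4.5% | 4.5% | 4.4% |
| Two v two, 0.5 SD | not recorded | 4.6% | 5.3% |
| Two v two, 1 SD | 61% | 7.2% | 8.8% |
| Two v two, 2 SD | 99.8% | 7.8% | 9.8% |
| One v three, 1 SD | 47% | 8.6% | 10.2% |
| One v three, 2 SD | 98% | 10.0% | 12.3% |
| One equal pair, others 5 SD apart | 100% | 3.9% | 5.2% |

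At 0.5 SD, one versus three gives 5.2–5.8%. Independent repeats at 2 to 5 SD gave 7.8% exact and 9.4–9.7% approximate for two versus two, and 10.0–10.1% and 12.4–12.5% for one versus three. If all four groups differ there is no true null pair and the error is zero.

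**6. Unequal groups.** Splits of 36 such as 12/8/8/8, 12/12/6/6 and 10/10/10/6 gave about 8–13% at 2 SD.

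**7. Across the three markers (a separate question).** With no differences and independent markers, 1 − (1 − 0.044)³ = 12.6%, or 9% at marker correlation 0.8. With a 2-SD partial pattern in one marker and none in the other two, 15–20% (correlation 0–0.5). With such a pattern in all three, 16–33% (correlation 0–0.8).

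**The case against.** The strongest reply is that this is a small first study with no hypothesis, primary marker or priority pair. The gate works under the global null, and strict family-wise control is partly a matter of convention. The excess also depends on the pattern: it needs two or three equal pairs and a sizeable difference, and the document supplies no effect size, SD or group sizes. Part of the upper end comes from the approximation. At 9 per group, U = 18 gives p = 0.0469 without continuity correction and 0.0521 with it, so an exact or corrected test stays at about 7.8% and 10%. Finally, a closed rule is elaborate for so short a plan.

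Much of this stands as a limit on size. The excess is conditional, moderate and absent in some patterns, and the three-marker figures should not be used to enlarge a within-marker point. None of it removes the problem. The two-equal-pairs result follows from structure, and the exact test still gives 7.8–10.0% at 2 SD. The plan does not call its pairwise results exploratory; they are the only route to the primary objective. Control at 5% has to hold whichever pattern is true, since the true pattern is unknown beforehand.

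**Conclusion.** The concern holds. Followed as written, the plan does not keep the chance of a false pairwise difference within a marker at 5%. At clear differences (2 SD or more) with 9 per group, that chance is about 8–10% when two equal pairs remain and 10–12.5% when three groups are equal, or roughly 1.5 to 2.5 times nominal. At 1 SD it is 7.2–10.2%. There is no excess with no differences or with one equal pair left, and little or none at 0.5 SD. The figures rest on assumed group sizes, two-sided tests and a shift model; unequal splits move the 2-SD range only to about 8–13%. The design remains valid, but the pairwise claims lack the error rate that the stated threshold implies, and this should be fixed.

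**What to change.** Keep both tests and add a closed rule within each marker. Declare a pair different only if all of these are significant at 0.05, except where another level is given:
- the four-group Kruskal-Wallis test;
- both three-group Kruskal-Wallis tests that contain the pair;
- the two-pair step: the smaller p-value of this pair and its complementary pair is below 0.025;
- the exact Mann-Whitney test for the pair.

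State that this controls error at 5% per marker only. In simulation it gave 3.0–5.0% in every setting with two or more equal pairs. Holm over the six pairs, or Dwass-Steel-Critchlow-Fligner p-values, would be simpler; no power was computed for the latter.

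If control over all three markers is wanted, apply the same rule with every threshold divided by three (0.0167, and 0.0083 for the two-pair step), or Holm over all 18 p-values. Simulated study-wise error was 2.2–4.6% and 1.4–4.4%. Holm on the three omnibus p-values does not control the pairwise claims: combined with the per-marker closed rule it still left 13–14% at 2 SD with independent markers.

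The cost is two or three sentences, no new data, and some power. Power per truly different pair (two versus two, 9 per group, exact test for the plan):

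| Rule | 1 SD | 1.5 SD | 2 SD |
|---|---|---|---|
| Plan | 39% | 78.5% | 96% |
| Closed rule, per marker | 32% | 73% | 95% |
| Holm, six pairs | 22% | 58% | 88% |
| Closed rule at 0.05/3 | 16% | 52% | 86% |
| Holm, 18 pairs | 12% | 39% | 76% |

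At 1 SD the per-marker closed rule loses (39 − 32)/39 = 18% of the plan's power, nearer a quarter if the plan would have used the approximation (about 42%). Holm over six pairs loses (39 − 22)/39 = 44%.

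If the pairwise results are meant as exploratory, the plan should say so and report all 18 p-values. That costs no power, but it changes the claim and does not control the error.
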